## Data management and quality assurance

A unique *Case Report Form* will be provided to all participating centers. There will be no possibility of adapting, changing or adding any different data to those gathered in the CRF. Although investigators from this hospital network in Spain have participated in a substantial number of studies collecting data either prospectively or retrospectively from charts, and in order to comply with data quality requirements, investigators will be trained in the use of CRF in advance (Lanas et al. Am J Gastroenterol 2009, ENERGIB study). Based on a sample of patients, investigators will also have to confirm in advance that medical records are compatible with the required data collection of the CRF. Furthermore, each CRF will be monitored for data consistency and accuracy. A sample of data recorded in the CRF from patients from each study centre will be evaluated by the study coordinator.

A specific computer program will be developed for data entry of each individual item collected in the CRF. Trained and experienced staff in managing databases will carry out the data entry. The database will be designed to minimize data entry errors,

In order to guarantee the confidentiality of the patients' data, only the hospital personnel will have access to the medical records. The study physicians will review the clinical charts and will fill in the data collection sheet with the relevant information. The clinical identification number will be recorded in the database

for data management purposes, but it will not be exported to the data analysis files to guarantee the patients' confidentiality. During the data entry process, a random fictitious identification number is created for each case, which will be the only identification available in the analysis files.

When the data collection and entry are completed, the information in the database will be exported to statistical analysis software, which will only contain the patients' fictitious identification created in the data entry process and not the clinical identification number, therefore preserving the patients' confidentiality during the data analysis process.

## **Statistics**

Sample size. Based on a recent international observational study on PUBs (Energib) the estimated re-bleeding rate was over 8% and the overall mortality rate of PUBs around 5%. It is assumed that these proportions will be increased between 1.5- and 2-fold in patients with high-risk stigmata that represent approximately between a third and a fourth of our total PUB study population. Assuming a 1.25% error for the lowest proportion and a 2.5% for the largest one, with an alpha value of 0.05, we have estimated a sample size of 1100 patients per group of PPI treatment for the overall PUB cohort to be studied and 400 - 500 per group (esomeprazole and pantoprazole) for those with high-risk stigmata.

Due to the study design, variables will be presented by descriptive statistics. Categorical data will be reported as frequencies and proportions. Continuous data will be reported as means and standard deviations. Where appropriate, alternate descriptive statistics such as quartile ranges, and medians with ranges for categorical and continuous data respectively will be reported. Analyses will be performed, overall, in patients with high-risk stigmata and according to individual PPI.

Although the objective of the study is to provide rates of outcomes of the different cohorts of PUB patients studied, potential differences in outcomes across different risk strata (age, co-morbidities, endoscopic findings, etc..) will be analysed with the Chi-square test for categorical variables and with t-test for continuous data. A variance analysis will be performed for multiple comparisons. Multivariable logistic regression models will also be fitted to define determinants of outcomes.

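### The 400–500 high-risk patients per PPI group cannot give the stated 2.5-point error at the protocol's own high-risk re-bleeding rate of 12–16%

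*Protocol*

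**What the plan says.** The Sample size paragraph of the Statistics section starts from an earlier observational study, in which "the estimated re-bleeding rate was over 8% and the overall mortality rate of PUBs around 5" per cent. For the high-risk subgroup, "It is assumed that these proportions will be increased between 1.5- and 2-fold in patients with high-risk stigmata", and these patients "represent approximately between a third and a fourth of our total PUB study population".

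The precision target follows: "Assuming a 1.25% error for the lowest proportion and a 2.5% for the largest one, with an alpha value of 0.05". From this, "we have estimated a sample size of 1100 patients per group of PPI treatment for the overall PUB cohort", and 400–500 per PPI group for patients with high-risk stigmata. The paragraph gives no formula and no sidedness, and does not say which proportion and error led to which size.

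The same section describes the aim as providing outcome rates. The Objectives section asks for the high-risk results (Objective 1) both overall and for each PPI, and re-bleeding is listed under Main outcomes.

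**The concern.** The protocol's own multiplier puts high-risk re-bleeding at 12–16% and high-risk mortality at 7.5–10%. Re-bleeding is therefore the largest proportion, whether one looks within the high-risk cohort or across both cohorts, and the 2.5% error should apply to it. A group of 400–500 looks too small for that.

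The protocol has no power calculation, effect size or margin, so the stated precision is the only justification for the numbers. If it is wrong for the high-risk cohort, the protocol promises per-PPI precision for Objective 1 that its own assumptions rule out.

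**Working it through.** **Inputs**, all from the Sample size paragraph: overall mortality 5%; overall re-bleeding 8% (stated as over 8%, so 8% is a floor); multiplier 1.5–2; error 1.25 points for the lowest proportion and 2.5 for the largest; alpha 0.05. Two assumptions are mine: the error is an absolute confidence-interval half-width, and alpha is two-sided.

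**Formulas.** n = 1.96² p(1−p)/d², rounded up, and half-width = 1.96 √(p(1−p)/n).

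**The overall size of 1100.**
- Mortality 5%, d = 0.0125: 3.8415 × 0.0475 / 0.00015625 = 1167.8, so 1168.
- At n = 1100 the half-width is 1.29 points at 5% and 1.60 points at 8%. A rate of 4.7% gives 1.25 points at about n = 1100.

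**The high-risk size of 400–500.**
- Rates: 8% × 1.5 = 12% and 8% × 2 = 16% for re-bleeding; 5% × 1.5 = 7.5% and 5% × 2 = 10% for mortality.
- Re-bleeding 12%, d = 0.025: 3.8415 × 0.1056 / 0.000625 = 649.1, so 650.
- Re-bleeding 16%, d = 0.025: 3.8415 × 0.1344 / 0.000625 = 826.1, so 827.

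**Half-width delivered in high-risk patients (points).**

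| n | mortality 7.5% | mortality 10% | re-bleeding 12% | re-bleeding 16% |
|---|---|---|---|---|
| 400 per PPI | 2.58 | 2.94 | 3.18 | 3.59 |
| 500 per PPI | 2.31 | 2.63 | 2.85 | 3.21 |
| 800 pooled | 1.83 | 2.08 | 2.25 | 2.54 |
| 1000 pooled | 1.63 | 1.86 | 2.01 | 2.27 |

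For re-bleeding per PPI, the interval is between 2.85/2.5 = 1.14 and 3.59/2.5 = 1.44 times as wide as stated.

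**Which rate would give 400–500 at 2.5 points?** Solving for p gives 7.0% at n = 400 and 8.9% at n = 500. Two candidates fall in that range: the un-inflated re-bleeding rate of 8% (452.4, so 453), and inflated mortality from 7.5% (426.4, so 427) to about 8.9% (500).

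**Other readings of the calculation.**
- One-sided alpha 0.05: 458 at 12% but 582 at 16%, and only 823 for 5% at 1.25 points. It does not reproduce both stated sizes.
- Continuity correction: 689–866 at 12–16%, and 1247 for 5% at 1.25 points. The requirement rises.
- Wilson half-widths at 400–500: 2.85–3.59 points, practically unchanged.
- Error read as the full interval width: about 2,600–3,300 at 12–16%.

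**Link to the high-risk share.** A fourth to a third of 1100 is 275–367 high-risk patients per PPI, below 400–500. The re-bleeding half-width is then 3.32 (n = 367, 12%) to 4.33 points (n = 275, 16%).

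**The case against.** Several points on the other side are fair.

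- **The overall size.** A reader might infer that 1100 is also wrong, because 5% at 1.25 points needs 1168. The protocol says around 5%, and the difference is 0.04 points of half-width. That is rounding, and the multiplier, which applies only to high-risk patients, has no part in it. Nor does the protocol promise 1.25 points for re-bleeding: that error belongs to the lowest proportion, and 1.60 points at 8% lies well inside 2.5.
- **The cause.** A reader might infer that the 1.5- to 2-fold increase was forgotten, since the un-inflated 8% falls inside 400–500. The protocol does not show which rate was used, and inflated mortality fits as well. That second reading would attach the 2.5% error to the smaller of the two high-risk rates, so it does not rescue the sentence, but it leaves the cause unproven.
- **Objective 1 as a whole.** Its pooled estimate would meet 2.5 points or come within 0.04 of it if 400–500 per PPI were reached. The shortfall concerns the individual-PPI estimates only. It does not disappear, because the sizes are stated per group and Objective 1 asks for individual-PPI rates.
- **Consequence.** The study is descriptive and retrospective. The shortfall of 0.35–1.09 points biases no estimate, and a reported confidence interval would show the precision obtained.

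What stands against the objection is that the protocol states inputs and a result that disagree. This is not detail that could be left to an analysis plan.

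**Conclusion.** Wrong as written, for the high-risk size only. At the protocol's own 12–16%, a 2.5-point error needs 650–827 patients per PPI group. The stated 400–500 delivers 2.85–3.59 points, 14% to 44% wider than claimed, and misses the target at every combination of the stated ranges. As the source rate is given as over 8%, the shortfall is if anything larger.

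The result rests on a two-sided 95% interval and on reading the error as an absolute half-width; none of the variants tried reproduces both stated sizes. The documents support neither a claim that 1100 is materially wrong nor a firm statement of how 400–500 arose. The total cannot be cross-checked either, because the target in Study design and patients is blanked in the public copy.

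**What to change.** In the Sample size paragraph:

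- For each cohort, name the proportion, error and sidedness behind the stated size.
- Replace the 2.5% claim for high-risk patients with the precision delivered at 400–500 per PPI: about ±2.9 to 3.6 points for re-bleeding at 12–16%, and ±2.3 to 2.9 points for mortality at 7.5–10%. The pooled re-bleeding figure (about ±2.0 to 2.5 points at 800–1000) can be added for the overall part of Objective 1.
- If the high-risk number is simply a fourth to a third of 1100 (275–367 per PPI), state ±3.3 to 4.3 points for re-bleeding instead.
- Keep 1100, with ±1.29 points at 5% mortality and ±1.60 at 8% re-bleeding.

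The 2.5% figure should not be kept by tying it to rates of 7–9%, since that would hide the mismatch with the assumed 12–16%.

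The cost is wording only, with no added patients. The one downside is a less favourable stated precision.

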## **Objectives:**

1. To assess outcomes in clinical practice in patients hospitalized due to PUB and treated with high-dose IV infusion PPI plus standard endoscopy therapy in patients with endoscopic high risk stigmata (spurting bleeding, visible vessel, oozing bleeding, red clot attached to the ulcer niche): overall and among individual PPI (esomeprazole and pantoprazole).

2. To assess outcomes in clinical practice in patients hospitalized due to PUB and treated with IV infusion PPI plus endoscopy therapy, if needed: overall and among individual PPI (esomeprazole and pantoprazole).

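### The sample-size paragraph is not reconciled: at its own high-risk share, 1100 patients per PPI group are expected to contain 275–367 with high-risk stigmata, not 400–500

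*Protocol*

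**What the plan says.** The sample-size paragraph in the protocol's Statistics section fixes three numbers:

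- an overall size and a high-risk size, both per PPI: "1100 patients per group of PPI treatment for the overall PUB cohort to be studied and 400 - 500 per group", the second applying to each of the two groups ("esomeprazole and pantoprazole) for those with high-risk stigmata");
- a share, given as "high-risk stigmata that represent approximately between a third and a fourth of our total PUB study population".

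The precision basis is stated as "Assuming a 1.25% error for the lowest proportion and a 2.5% for the largest one, with an alpha value of 0.05". The base rates are re-bleeding of just over 8% and mortality of about 5%, and it is assumed that "these proportions will be increased between 1.5- and 2-fold in patients with high-risk stigmata".

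Under Methods, Study design and patients, eligible patients are a consecutive series identified by diagnosis codes. The Statistics section analyses that series as a whole, in its high-risk part and by PPI. Neither section describes oversampling or a separate intake of high-risk patients.

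Objective 1 concerns patients "treated with high-dose IV infusion PPI plus standard endoscopy therapy in patients with endoscopic high risk stigmata" and asks for results both over the two PPIs together and for each PPI.

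**The concern.** The high-risk patients are a subset of a consecutive cohort, so their expected number follows from the cohort size and the share. The paragraph states all three quantities, and the third does not follow from the other two.

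Two things depend on it. First, inclusion runs until the desired sample size is complete, and the paragraph leaves unclear whether that means 1100 per group or 400–500 high-risk patients per group. Second, Objective 1 is the protocol's first objective, and a reader will take 400–500 per PPI as the basis for the precision of its rates. If inclusion stops at 1100 per group, those rates will be estimated from fewer patients than stated.

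**Working it through.** **Inputs**, all from the Statistics section: 1100 per PPI group; 400–500 high-risk per PPI group; share 1/4 to 1/3; base rates 8% (re-bleeding) and 5% (mortality); multiplier 1.5–2; errors of 1.25 and 2.5 points; alpha 0.05. The high-risk rates are therefore 8% × 1.5 to 2 = 12–16% for re-bleeding and 5% × 1.5 to 2 = 7.5–10% for mortality.

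**Step 1. The plan's own figures.** For one proportion, n = z²p(1−p)/d², with z = 1.96 (two-sided).

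- p = 5%, d = 1.25%: n = 1168, against the stated 1100. The stated figure corresponds to p ≈ 4.7%, which is close to the protocol's approximate 5%.
- d = 2.5%: n = 426 at 7.5% and 452 at 8%, both inside 400–500; but 553 at 10%, 649 at 12% and 826 at 16%. The range 400–500 corresponds to p of about 7.0–8.9%.
- One-sided, n = 823 for p = 5%, d = 1.25%; with d = 2.5%, n = 390 at 10%, 457 at 12% and 582 at 16%.

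No single convention returns both stated figures exactly. The two-sided reading comes close to 1100, and it returns 400–500 only for a proportion near 7–9%.

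**Step 2. Expected high-risk yield.**

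- 1100 × 1/4 = 275; 1100 × 1/3 = 367 per PPI group.
- Both PPIs: 2200 × 1/4 = 550; 2200 × 1/3 = 733.
- Gap per group: from 400 − 367 = 33 (8% of 400) to 500 − 275 = 225 (45% of 500).
- Share needed within 1100: 400/1100 = 36.4%; 500/1100 = 45.5%.
- Patients per group needed at the stated share: 400 × 3 = 1200 to 400 × 4 = 1600; 500 × 3 = 1500 to 500 × 4 = 2000.

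**Step 3. Precision.** Half-width = 1.96 × √(p(1−p)/n), in percentage points:

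| High-risk n | p = 7.5% | p = 10% | p = 12% | p = 16% |
|---|---|---|---|---|
| 275 (per PPI) | 3.11 | 3.55 | 3.84 | 4.33 |
| 367 (per PPI) | 2.69 | 3.07 | 3.32 | 3.75 |
| 400 (stated) | 2.58 | 2.94 | 3.18 | 3.59 |
| 500 (stated) | 2.31 | 2.63 | 2.85 | 3.21 |
| 550 (pooled) | 2.20 | 2.51 | 2.72 | 3.06 |
| 733 (pooled) | 1.91 | 2.17 | 2.35 | 2.65 |

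The smallest loss from the shortfall is 2.69 − 2.58 = 0.11 points (367 against 400, at 7.5%). The largest is 4.33 − 3.21 = 1.12 points (275 against 500, at 16%).

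At the stated 400–500, the 2.5-point error is met only towards 500 and at the lowest rate, 7.5%.

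**The case against.** **1100 need not be a cap.** The paragraph can be read as giving two separate minimum requirements, with enrolment driven by the larger. A reader might infer from the arithmetic that 400–500 high-risk patients per group are unattainable, but the document does not establish that. The overall target under Study design and patients was a range whose figures are missing from the text shown, so it cannot be known whether it covered 1200–2000 per group. This stands, and limits the point to an expected yield at the stated share. It does not reconcile the paragraph, which gives 1100 and no larger number.

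**Which figure is wrong is open.** It is tempting to say that the high-risk size is overstated. The overall size could equally be too small, or the share too low. The text does not decide.

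**The precision gap has two sources.** A reader might set 3.3–4.3 points against 2.5 and blame the shortfall for the whole difference. That is not supported: 400–500 patients already give 2.8–3.6 points at the re-bleeding rates. The protocol also ties 2.5% only to the largest proportion, so applying it to high-risk mortality is an interpretation.

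**The lower end is close.** The share is approximate, and 36.4% is not far from 33.3%. This could excuse 400, but hardly 500, which needs 45.5%. The 45% gap pairs the lowest share with the highest target and is an extreme.

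**The study is descriptive.** Its stated aim is to report outcome rates, and no power claim for a PPI comparison rests on 400–500. That limits the harm to wider intervals and an unclear target.

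Reading 400–500 as a total over both PPIs does not help: the text says per group, and 2200 patients would give 550–733.

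**Conclusion.** The point holds as an internal inconsistency in the sample-size paragraph. At the protocol's own share, 1100 per PPI group is expected to contain 275–367 high-risk patients, and that range does not overlap 400–500. The expected half-widths per PPI are 3.3–4.3 points for re-bleeding and 2.7–3.6 for mortality, against 2.8–3.6 and 2.3–2.9 at the stated size. The shortfall accounts for about 0.1–1.1 points. The remaining excess over 2.5 points comes from an error that 400–500 patients would mostly not deliver at the assumed high-risk rates.

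This rests on the stated share and rate multipliers, two-sided 95% intervals with the normal approximation, independent patients, and inclusion ending at 1100 per group. Objective 1 also requires high-dose PPI and endoscopic therapy, so its cohort would be no larger than the high-risk count. How much smaller cannot be said, because the protocol gives no frequency for either treatment.

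**What to change.** Restate the sample-size paragraph so that the overall size, the share and the high-risk size agree.

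If 1100 per PPI group is kept:

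- give the expected number with high-risk stigmata as 275–367 per PPI group and 550–733 over both;
- say that this count is taken before requiring high-dose PPI and endoscopic therapy;
- replace the 2.5% error for the high-risk patients with the half-widths delivered, for both levels that Objective 1 asks for: per PPI, 3.3–4.3 points for re-bleeding and 2.7–3.6 for mortality; pooled, 2.4–3.1 and 1.9–2.5.

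If a different share or a larger overall target was intended, state it so that the three numbers are consistent. At the present share, 400–500 high-risk patients per group imply 1200–2000 per group overall.

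Cost with 1100 kept: wording only and no added patients, but the stated high-risk precision becomes less favourable. Choosing the larger target instead would mean 100–900 more patients per group (1200 − 1100 to 2000 − 1100).

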## **Methods**

## Study design and patients

This will be a multicenter retrospective observational study carried out in Spain. In order to prevent selection bias in pharmacotherapy, participating centers will be selected if they use routinely a single IV PPI (esomeprazole or pantoprazole) in the management of PUB events.

The eligible patients will be all consecutive patients hospitalized due to PUB and selected according to codes from ICD9 which identify gastric and duodenal ulcer bleeding (Table I). Patients will be included retrospectively from

till completion of the desired sample size, which was estimated to be between ).

Eligible patients will be those complying with the following characteristics: a) age (≥18 years) admitted to the hospital with an overt upper GI bleed due to peptic ulcer and manifested as hematemesis/coffee ground vomiting, melena, hematochezia and other clinical or laboratory evidence of acute blood loss from the upper GI tract; b) evidence that an upper GI endoscopy was performed; c) IV PPI (esomeprazole or pantoprazole) had to be used after the endoscopy procedure d) complete medical records available for the study-related

3

hospitalization. Exclusion criteria are: patients with terminal malignant disease (life expectancy less than 6 months), required treatment with ASA or NSAIDs for the next 3 days during hospital after endoscopic therapy, or suffering from haematological disease associated with severe dyscrasia (e.g haemophilia)

Information regarding patient's characteristics, drug use before the PUB event, co-morbidities, symptoms, signs and severity of the event at hospital admission, endoscopic findings, endoscopic therapy, pharmacological therapy including type of drug, dose, route an type of administration, and outcomes will be collected from each patient's hospital medical records.

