## Data, measurements and endpoint definitions

We will collect data recorded in charts in a pre-specified Case Report Form. Main data from each patient will include demographics, diagnostic procedures and both non-pharmacological and pharmacological treatments received by patients as summarized in Table II.

Therapeutic endoscopy will be considered any endoscopic action (injection, clips, thermo-coagulation, etc...) implemented to control the bleeding event in the presence of spurting bleeding, oozing bleeding, visible vessel, and/or clots attached to the ulcer niche. Endoscopic re-treatment will be considered when any repeated procedure occurred within 30 days from the index hospital admission due to re-bleeding from the PUB episode. High-dose IV PPI will be considered the administration of either esomeprazole or pantoprazole by infusion at the dose of 8 mg/hour. However, due to the variability of clinical practice and for the purpose of this study, the administration of equivalent doses of the PPI by injection within each 24-hour period will also be considered. The dose, route and type of administration will be recorded for each patient.

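### Objective 1 concerns a treated high-risk group, but the Statistics section names and sizes that group by stigmata only

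*Protocol*

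**What the plan says.** Under Objectives, the first objective concerns patients "treated with high-dose IV infusion PPI plus standard endoscopy therapy in patients with endoscopic high risk stigmata". The second concerns those "treated with IV infusion PPI plus endoscopy therapy, if needed". The second drops the high-dose condition and makes endoscopic therapy conditional, so the two objectives describe different treatments.

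Eligibility (Study design and patients) asks for "evidence that an upper GI endoscopy was performed" and states that "IV PPI (esomeprazole or pantoprazole) had to be used after the endoscopy procedure". It sets no dose and no mode of administration, and it does not require the endoscopy to be therapeutic.

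The section on data, measurements and endpoint definitions defines therapeutic endoscopy, and it defines the high-dose regimen: "High-dose IV PPI will be considered the administration of either esomeprazole or pantoprazole by infusion at the dose of 8 mg/hour". It then widens that definition, citing variable practice: "the administration of equivalent doses of the PPI by injection within each 24-hour period will also be considered". It adds that "The dose, route and type of administration will be recorded for each patient".

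Statistics gives the analysis sets in one sentence: "Analyses will be performed, overall, in patients with high-risk stigmata and according to individual PPI". It plans 1100 patients per PPI group overall and 400-500 per PPI group in the high-risk stratum, which it identifies by stigmata.

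**The concern.** Objective 1 has three conditions: stigmata, high-dose PPI and endoscopic therapy. The set that should serve it carries only the first. Eligibility does not supply the other two, and nothing in the protocol uses its definitions of high-dose PPI or therapeutic endoscopy to form a set. A patient with a visible vessel, no endoscopic therapy and a lower PPI dose meets the eligibility wording and falls in the stigmata stratum.

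The protocol expects such patients. Its Introduction says that the uptake of the recommendations in practice is not known, and its dose definition is widened because practice varies. A rate for everyone with stigmata is a legitimate quantity, but it answers a different question from Objective 1. The stated precision also belongs to the larger group.

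**Working it through.** **The sets side by side**

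| Condition | Objective 1 | Eligibility | High-risk set in Statistics |
|---|---|---|---|
| High-risk stigmata | yes | no | yes |
| Therapeutic endoscopy | yes | no (endoscopy only) | not stated |
| High-dose PPI | yes | no (any IV PPI) | not stated |

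The mismatch needs no arithmetic. The calculations below only show how much it could matter.

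**The plan's own figure.** Precision formula: n = 1.96² × p(1 − p) / e², two-sided alpha 0.05, with e read as percentage points.
- Overall set, p = 5%, e = 1.25 points: n = 1168, against the stated 1100.
- High-risk set, e = 2.5 points: p = 7.5% (mortality 5% × 1.5) gives 427, and p = 8% gives 453. Both lie within 400-500.
- High-risk re-bleeding, e = 2.5 points: p = 12% (8% × 1.5) gives 650, and p = 16% (8% × 2) gives 827. Both lie outside.

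The 400-500 is thus reached only near 7.5-8%. It counts patients with stigmata and makes no allowance for those without the combination.

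**Shift in the reported rate.** Let p be the rate in patients with the full combination, s the share of the stigmata group without it, and RR their relative risk. Then

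reported rate − Objective 1 rate = p × s × (RR − 1).

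The documents give neither s nor RR. I assume s = 10-50% and RR = 0.7-2, with p = 12% as an illustration. Remaining n per group is 400(1 − s) or 500(1 − s). The 95% half-width is 1.96 × √(0.12 × 0.88 / n).

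| s | n from 400 (half-width) | n from 500 (half-width) | Shift, RR 0.7 | RR 1 | RR 1.5 | RR 2 |
|---|---|---|---|---|---|---|
| 10% | 360 (3.4) | 450 (3.0) | −0.4 | 0 | +0.6 | +1.2 |
| 30% | 280 (3.8) | 350 (3.4) | −1.1 | 0 | +1.8 | +3.6 |
| 50% | 200 (4.5) | 250 (4.0) | −1.8 | 0 | +3.0 | +6.0 |

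Half-widths and shifts are in percentage points. Without any restriction, the half-width at 12% is 3.2 points with 400 patients and 2.9 with 500.

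The same formula at the high-risk mortality rates implied by the protocol (5% × 1.5 = 7.5% and 5% × 2 = 10%) gives about −1.1 to +3.8 points and −1.5 to +5.0 points.

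**What the 12% is.** Statistics applies its 1.5-2-fold increase to all patients with stigmata, so 12% is strictly a rate for the mixed group. If it is used that way, the Objective 1 rate is 12 / (1 + s(RR − 1)). At s = 50% and RR = 2 this is 12 / 1.5 = 8.0%, a shift of +4.0. At s = 50% and RR = 0.7 it is 12 / 0.85 = 14.1%, a shift of −2.1. The order of magnitude is unchanged.

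**Re-bleeding.** The outcome definition presupposes successful initial endoscopic treatment. Read literally, a patient who had none cannot have the event. If 20% of the denominator had no endoscopic therapy and the rest re-bled at 12%, the reported rate would be 0.8 × 12 + 0.2 × 0 = 9.6%, a shift of −2.4 points. This is RR = 0, outside the grid above. A lower PPI dose could act in either direction. The definitions of surgery and mortality have no such condition, so those rates mix on both treatments.

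**The case against.** The sentence in Statistics is a short list of cuts and does not say that stigmata are the sole criterion. Objective 1 already states its population, the terms are defined elsewhere, and building the set could be left to a statistical analysis plan. The data are collected, so nothing is lost. This tempers the urgency. It does not remove the point, because the protocol is not silent: it names the set and sizes it, and a plan that followed it would report a rate for another population.

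Several stronger readings are tempting, and the documents do not support them.
- A reader might infer that the reported rate is too high. The sign is unknown, and for re-bleeding it may be downward.
- A reader might take 12% as the documented rate in fully treated patients. The protocol gives it for all patients with stigmata.
- A reader might say that a comparison with the 5.9% recurrent bleeding of the cited randomised trial is spoiled. That figure is background, and no comparison with it is planned.
- A reader might infer that a patient whose infusion was cut short by death or surgery would drop out of the high-dose class. The infusion rule is a rate with no minimum duration, so it does not do this. The worry can apply only to injections, which are judged by equivalent dose per 24-hour period, and only once the definition is used to form a set.
- A reader might call the injection rule an error. It is a declared operational extension. What remains is that both objectives speak of infusion, so the texts must be reconciled.
- A reader might infer that the two PPI groups received different treatment mixes. That is possible, but nothing in the protocol shows it.

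**Conclusion.** The point stands as a mismatch between Objective 1 and the set that the Statistics section names and sizes. Followed as written, the high-risk surgery and mortality rates describe patients with stigmata whatever their PPI dose or endoscopic therapy, and the re-bleeding rate may have a denominator containing patients who cannot have the event.

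The documents fix neither the size nor the direction of the effect. The range of about -1.8 to +6.0 points at 12% rests wholly on the assumed 10-50% without the combination and the assumed relative risk of 0.7-2. For scale, the protocol's stated error for its largest proportion is 2.5 points. The effect is nil if every patient with stigmata received both treatments, or if the risks are equal. The definitional mismatch does not depend on these assumptions.

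**What to change.** In Statistics:
- Define the Objective 1 set as patients with high-risk stigmata AND therapeutic endoscopy at the index endoscopy AND the high-dose regimen as the protocol itself defines it.
- Classify the regimen by what was started after the index endoscopy, so that early death or surgery cannot change the class of patients given injections.
- Report patients with stigmata who did not get the combination in a separate row with their number, and keep the stigmata-only rate beside the Objective 1 rate.
- Restate the precision for the smaller Objective 1 set.

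Separately, reconcile the infusion wording in the Objectives with the rule that counts equivalent injections. Which of the two should prevail is for the sponsor and investigators to settle.

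The cost is wording, one further table and a revised precision statement. No new data are needed, because dose, route, type of administration and endoscopic therapy are already on the list of variables. The price is a smaller set with a wider interval: under the assumed 10-50% without the combination, 200-450 patients per PPI group and a half-width of about 3.0-4.5 points at 12%.
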